1.0 BACKGROUND

Positron Emission Tomography (PET) is the gold standard for non-invasive measurement of resting myocardial blood flow (rMBF) and stress myocardial blood flow (sMBF) (1,2). Measurements of MBF by PET using the radionuclides rubidium-82 (Rb-82), nitrogen-13 ammonia (N-13) or oxygen-15 labeled water have been well correlated with direct invasive measurements via doppler velocity and flow wires. The constellation of data has validated the upper limits of rMBF and sMBF in healthy, young volunteers as well as the lower limits in tissue with transmural myocardial infarctions (MI)(3-8). Furthermore, test-retest methodological precision of global PET myocardial perfusion by serial rest or stress PET minutes apart using a standard infusion bolus as measured of a 2D PET scanner is $\pm 10\%$.(9) Rb-82 and N-13 are the only FDA approved radiopharmaceuticals for myocardial perfusion imaging. Currently, Rb-82 is the preferred radiopharmaceutical at Ochsner. Given Rb-82's ultra-short half-life of 76 seconds, quantification of MBF poses significant challenges on contemporary 3D PET systems.

An estimated 95% of installed PET scanners are used mainly for whole-body ^{18}F -fluorodeoxyglucose (FDG) oncology applications. Therefore, these systems have not been designed historically with the performance specifications required to achieve accurate MBF quantification and to maintain high quality myocardial perfusion imaging. As opposed to most clinical PET applications that perform static imaging at some delayed time after the tracer biodistribution has stabilized, MBF quantification requires the acquisition of dynamic images starting immediately from time of tracer administration and including the biophysical distribution process.

During early time phase of the acquisition, almost all tracer activity is concentrated in a small bolus of the venous system contained within the scanner field of view resulting in very high detector count rates that risk saturating the photon detection and processing subsystems. In contrast, during late

phases of the acquisition, the activity is distributed widely throughout the body tissues, and only a small fraction of the administered activity resides within the heart and adjacent organs in the scanner field of view. Furthermore, for short-lived tracers such as ^{82}Rb , the isotope activity will decay several half-lives over the course of imaging. Consequently, late-phase count rates (perfusion images) can be orders of magnitude lower than those of the early-phase, risking low-quality perfusion images that are noisy and require the use of smoothing filters at the expense of spatial resolution and image contrast(10). Therefore, for each 3D camera, there is an ideal range of administered Rb-82 activity such that detector saturation is avoided, and perfusion images are diagnostic(11).

Furthermore, during 3D acquisition, there is significant scatter and random detections that are corrected for within the sub-processing systems. These events occur much more frequently with higher activities and are non-linear with decay. Hence, with short lived tracers such as Rb-82, the scatter and random corrections must occur at short intervals (5-10 seconds) and images created from the summed scatter and random corrected intervals(12). The necessary processes to achieve accurate and diagnostic images requires a tremendous amount of computational power and time.

Reconstruction times on first generation 3D PET/CT could take ~45 minutes per dataset when using 5 second intervals. Therefore, a 3/9/22 Rb-82 infusion profile (20mls/min) was developed: 1) to mitigate scatter and the lengthy processing time 2) to mitigate detector saturation 3) to maintain diagnostic quality perfusion images 4) to obtain accurate MBF data. However, on modern day 3D PET/CT scanners with faster internal components and improved processing speeds, the necessity of the low flow profile vs. the standard profile (50mls/min bolus) is under debate. We seek to test these profiles on 3 distinct populations of volunteers.

2.0 Rationale and Hypotheses

As perfusion metrics in the healthy volunteers, patients with risk factors and/or coronary artery disease and in tissue with transmural myocardial infarctions has been well defined(13) AND same day test-retest variability minutes apart using a bolus infusion is $\pm 10\%$ (9), we shall test 3 hypotheses.

The first hypothesis is repeated same day test-retest coefficient of variation (COV) of whole heart rMBF and sMBF acquired using a bolus on a modern 3D PET scanner falls within $\pm 10\%$. The second hypothesis is repeated same day test-retest COV of whole heart rMBF and sMBF acquired using a low flow profile on a modern 3D PET scanner falls within $\pm 10\%$. The third hypothesis is COV of whole heart rMBF and sMBF between bolus and low flow profile is $\pm 10\%$ where the bolus is considered the standard on a modern 3D PET scanner.

The above testing and hypotheses deal with precision of MBF measurements however does not address accuracy. Measuring accuracy of non-invasive MBF measurements poses significant challenges as a “gold standard” for comparison is not realistically achievable in a clinical setting. Invasive measurements would pose unnecessary risk for patients and non-invasive “gold standard” measurements would require a standardized “phantom pump” which is not available within industry. Instead, PET labs have traditionally relied on patient populations to determine accuracy. As such, this study will not test nor is it powered to answer questions regarding accuracy. As the PET camera is currently being installed and testing prior to a “clinical go-live” is preferable to ensure measured flow metrics are consistent with the literature, as part of quality assurance, testing of the above hypotheses will also allow us to make additional observations to:

- 1) Confirm healthy volunteers measured rMBF and sMBF fall within published ranges (rMBF 0.69-1.06 cc/min/g and sMBF >2.17cc/min/g) .(13)
- 2) Confirm clinical volunteers with risk factors and/or CAD measured rMBF and sMBF fall within published ranges (rMBF 0.50-1.10 cc/min/g and sMBF >1.09 to 2.17 cc/min/g).(13)

- 3) Confirm rMBF in regions of infarct in volunteers with prior large myocardial infarctions fall within published ranges (rMBF <0.45 cc/min/g with minimum <0.19 cc/min/g).(14)

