7.0 Statistical Analysis

This is a measurement reliability study in a 2x2 factorial design. Study factors are infusion flow rate (20 or 50) at rest and stress. The linear nature of data acquisition takes about 45 minutes and yields five absolute values for each subject: three resting values and 2 stress values. The first 2 resting values and the 2 stress values condition are obtained in a cross-over fashion by infusion flow rate (infusion level assigned randomly for first resting scan and for first stress scan). The third resting value will be obtained at either a 20 or 50 infusion flow rate and will be used to determine precision (test-retest variability) against the same infusion profile obtained in the first two infusions.

Precision and variability will be determined for global, average quadrant, and individual pixel values of rest flow, stress flow and CFR. Standard summary statistical tests will be used. Applicable tests are 2-tailed, and $p < 0.05$ will be considered statistically significant. Linear regression will be reported between rest perfusion and rest pressure rate product (PRP). Paired or unpaired Student *t* test will be used to evaluate continuous variables where appropriate. The Pitman-Morgan *F* test will be used to test for differences in variability of perfusion between groups. To compare the histogram distribution between groups of stress perfusion and CFR for each of 1344 pixels as percentage of LV in color-

coded ranges of coronary flow capacity, we will use the Kolmogorov-Smirnov (KS) test for differences in histogram distribution.

8.0 Reporting of Adverse Events or Unanticipated Problems involving Risk to Participants or Others

Adverse events or unanticipated problems will be reported to [name] or [name] at [contact] and the Internal Review Board as directed by Ochsner Medical Center IRB rules and regulations.

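### Hypotheses 1 and 2 claim same-profile repeatability for stress flow, but the design has no same-profile stress repeat; the COV to be compared with 10% is also undefined

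*Combined protocol and SAP*

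**What the plan says.** Section 2.0 sets three hypotheses, each with a ±10% limit and each covering both rest and stress flow.

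- Hypothesis 1 concerns the bolus: "The first hypothesis is repeated same day test-retest coefficient of variation (COV) of whole heart rMBF and sMBF acquired using a bolus". Hypothesis 2 makes the same claim for the low-flow profile.
- Hypothesis 3 compares the profiles: "The third hypothesis is COV of whole heart rMBF and sMBF between bolus and low flow profile", with the bolus as reference ("where the bolus is considered the standard on a modern 3D PET scanner").

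Section 7.0 describes the data. Acquisition "yields five absolute values for each subject: three resting values and 2 stress values". On allocation: "The first 2 resting values and the 2 stress values condition are obtained in a cross-over fashion by infusion flow rate", with the order randomized. The third resting scan, at either rate, "will be used to determine precision (test-retest variability) against the same infusion profile obtained in the first two infusions".

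The same section promises: "Precision and variability will be determined for global, average quadrant, and individual pixel values of rest flow, stress flow and CFR". It names paired or unpaired t tests ("test will be used to evaluate continuous variables where appropriate"), the Pitman-Morgan test, linear regression and the Kolmogorov-Smirnov test. It gives no formula for COV and does not mention the 10% limit.

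**The concern.** A same-profile test-retest claim needs two scans of the same subject, in the same state, with the same profile. Section 7.0 provides that at rest only. Two of the four claims in Hypotheses 1 and 2 (bolus sMBF and low-flow sMBF) therefore have no repeat data, although section 7.0 still promises precision for stress flow and CFR.

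A second gap affects all three hypotheses. A limit of 10% on a COV is not a decision rule until three things are fixed: which SD is meant (within-subject, or of the paired differences), whether a systematic difference counts, and whether the estimate or a confidence limit must meet it. The plan settles none of these. What is at stake is whether a finding of within 10% has one meaning, and whether the stress claims have any direct support.

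**Working it through.** The documents give no sample-size calculation, SD or worked COV, so there is no stated figure to reproduce.

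**1. Counting pairs.** Let the first rest profile, the first stress profile and the third rest profile each be 20 or 50. That gives 2 × 2 × 2 = 8 sequences. In every one:

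| Pair type | Per subject | Over 80 subjects |
|---|---|---|
| Same-profile stress | 0 | 0 |
| Same-profile rest | 1, at one profile only | 80 (about 40 per profile if split evenly; the split is not stated) |
| Between-profile stress | 1 | 80 |

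The 80 is 85 enrolled less the first 5, whom section 3.0 leaves out of the final analysis. The saturation repeat in section 5.0 concerns the resting scan at another dose, so it adds no stress pair. Same-profile CFR repeatability needs a stress repeat too, so it is also missing.

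**2. Which SD?** Assume within-subject noise σ on the log scale. The log difference in a pair, d, is then N(δ, 2σ²), where δ is the log shift. Take σ = 8% (assumed), δ = 0, n = 80, and compare the estimate with 10%.

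- COV = SD(d)/√2: P(χ²₇₉ ≤ 79 × 0.10²/0.08² = 123.4) = 0.999.
- COV = SD(d): P(χ²₇₉ ≤ 79 × 0.10²/(2 × 0.08²) = 61.7) = 0.075.

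The plain-SD result depends strongly on the assumed noise: 0.57 at 7% and 0.003 at 9%. With 40 pairs, as for Hypotheses 1 and 2 at rest, the same formulas with 39 degrees of freedom give 0.986 and 0.166 at 8% noise.

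**3. Does an offset count? (Hypothesis 3)** SD(d)/√2 ignores δ. The RMS form, √(mean(d²)/2), includes it. Its underlying value is √(σ² + δ²/2), and its pass probability comes from a noncentral χ² with 80 degrees of freedom and noncentrality 80δ²/(2σ²).

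| Assumed noise | Assumed shift | Underlying RMS COV | SD(d)/√2 passes | RMS passes |
|---|---|---|---|---|
| 8% | ratio 1.15 (δ = 0.140) | 12.7% | 99.9% | 0.03% |
| 8% | δ = 0.10 | 10.7% | 99.9% | 20% |
| 5% | δ = 0.10 | 8.7% | about 100% | 99.6% |

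For ratio 1.15 across other noise levels, SD(d)/√2 passes about 100% of the time at 5% to 7%, 92% at 9% and 52% at 10%. RMS passes 2.2% at 5%, 0.2% at 7% and under 0.01% at 9% and 10%.

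**4. What the paired t test would show.** At δ = 0.05, σ = 8% and n = 80, the noncentrality is 0.05/(0.08√2/√80) = 3.95 and two-sided power is 97%.

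**5. Precision at rest.** With 40 pairs (39 degrees of freedom), an observed 8% has 95% limits 8 × 0.819 = 6.55% and 8 × 1.284 = 10.27%. With 38 degrees of freedom they are 6.54% and 10.31%. Either way, about 6.5% to 10.3%.

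**The case against.** - *The scan scheme is not visible.* True: sections 3.0 and 5.0 refer to an attached protocol, and a figure is not shown. But the text of section 7.0 is explicit on the number of stress scans and their allocation, and no other text supplies a same-profile stress repeat.
- *The cited source for the 10% may define the COV.* It may. This cannot be checked from the documents, so the second point is only that the plan itself does not define it.
- *A systematic offset would be noticed.* This largely stands. If the planned paired t test is applied to the profile pair, it would very probably detect even a 0.05 log shift at 8% noise. But it tests for zero difference and is not linked to the 10% limit, so it does not say whether Hypothesis 3 holds.
- *The study disclaims accuracy.* Section 2.0 does so because no external gold standard is available. Hypothesis 3 is an internal comparison with the bolus, so an offset from the bolus still matters.
- *Profile-specific stress noise could be recovered indirectly,* from the variances and covariance of the two stress scans. The plan does not propose this. In a simulation with assumed 8% error and 35% between-subject spread, a 10% proportional profile bias made the estimated bolus error variance negative in 89% of runs.

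A reader might also infer that the between-profile stress pair will be presented as evidence for Hypothesis 2, hiding a noisy low-flow profile, or that the formula will be picked after the data are seen. The documents support neither. Section 2.0 assigns the between-profile comparison to Hypothesis 3, and on the formula the plan is simply silent.

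**Conclusion.** The main point holds and needs no numerical assumption about noise or shift: with 0 of 80 same-profile stress pairs, the stress half of Hypotheses 1 and 2 cannot be tested directly as written. The rest half can be, and stress flow can be compared between profiles under Hypothesis 3.

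The secondary point also holds. COV is undefined, and the choice can decide the result. The √2 question reaches all three hypotheses; the treatment of a systematic offset bears chiefly on Hypothesis 3. All noise and shift values are assumptions, since the documents give none.

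It would go too far to say that the formula always decides: at 5% noise and a log shift of 0.10, both versions in the third check pass. It would also go too far to say that a shift would escape the planned analyses.

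**What to change.** 1. Reconcile sections 2.0 and 7.0. With the scans as written, restrict Hypotheses 1 and 2 to rMBF, state that same-profile sMBF and CFR repeatability is not tested, and assess sMBF only between profiles (Hypothesis 3).
2. Define COV once for all hypotheses as the within-subject SD (SD of paired log differences divided by √2), with a 95% CI.
3. For Hypothesis 3, separately for rest and stress, report the mean low-flow/bolus ratio with its 95% CI against a 10% margin that the sponsor confirms. Report the within-subject COV separately.
4. For Hypotheses 1 and 2 at rest, report beside the COV the mean difference between the third scan and its same-profile partner. Let the sponsor fix in advance whether such drift counts toward the 10%. This can matter: an assumed 9% noise with 8% drift is √(0.09² + 0.08²/2) = 10.6% if drift counts and 9.0% if it does not.
5. Fix in advance whether the estimate or its upper confidence limit must be below 10%. With 40 pairs, the estimate rule passes 85% of the time at a true 9% and 53% at a true 10%; a one-sided 95% upper-limit rule passes 21% and 5%.

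The cost is protocol and SAP wording and a short script. The stress half of Hypotheses 1 and 2 is given up, and the rest estimates remain imprecise, as the last check shows.

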3.0 Study Design and Population

This is a prospective, single center study from the Ochsner Medical Center. We seek to enroll a total of 85 paid volunteers that collectively encompass the range of physiology seen in routine practice. For simplicity sake, the range can be broken down into 3 distinct groups: 1) healthy volunteers without cardiac risk factors or chronic medical conditions (“normal”) 2) clinical patients with cardiac risk factors and/or history of clinical coronary artery disease (CAD), percutaneous coronary intervention (PCI) or coronary artery bypass grafting (CABG) (“clinical”) 3) patients with large myocardial infarctions demonstrated on prior PET stress testing (“infarct”). Volunteers will be recruited by “word-of-mouth” and through electronic records chart review. “Normal” volunteers will be consented and screened by history and laboratory tests for unrecognized cardiovascular risk factors, nicotine and caffeine. “Clinical” and “infarct” volunteers will not require laboratory tests other than caffeine levels. Once screened and consented, volunteers will undergo dipyridamole myocardial perfusion 3-D PET/CT stress testing with variable Rb-82 infusion profiles per the attached protocol. Female volunteers will also be questioned on their menstrual history and undergo urine pregnancy testing if appropriate on the day of the scan. The first 5 volunteers will be not be used in the final analysis but will be used to confirm proper scanner function, reconstruction settings and appropriate filter settings.

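### The three hypotheses set a 10% limit for a COV, but no planned analysis compares a COV with that limit or gives it a confidence interval

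*Combined protocol and SAP*

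**What the plan says.** Section 2.0 gives the published benchmark: "same day test-retest variability minutes apart using a bolus infusion is" ±10%. It then sets three hypotheses, each covering whole-heart resting flow (rMBF) and stress flow (sMBF):

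- Hypothesis 1: repeat COV "acquired using a bolus on a modern 3D PET scanner falls within" ±10%.
- Hypothesis 2: repeat COV "acquired using a low flow profile on a modern 3D PET scanner falls within" ±10%.
- Hypothesis 3: "The third hypothesis is COV of whole heart rMBF and sMBF between bolus and low flow profile is" ±10%, with the bolus as the standard.

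Section 7.0 is the only statistical section. It says "Standard summary statistical tests will be used" and then names linear regression of rest perfusion on pressure-rate product, paired or unpaired t tests, the Pitman-Morgan test for variability between groups, and the Kolmogorov-Smirnov test for histograms. The significance rule is generic: "Applicable tests are 2-tailed, and $p < 0.05$ will be considered statistically significant". The documents contain no COV formula, confidence interval, decision rule or sample-size justification. The one mention of power is a disclaimer about something else: "this study will not test nor is it powered to answer questions regarding accuracy".

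**The concern.** Each hypothesis claims that a quantity lies inside a fixed limit. The named tests look for a difference, an association or a difference in spread between groups. Pitman-Morgan comes closest, but it compares two variances with each other and not one COV with 10%. A non-significant result from any of these tests would not show that a COV is below 10%.

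That leaves the observed COV as the only evidence, with no allowance for its sampling error. The limit is also the benchmark's own value, so a camera exactly as precise as the benchmark sits on the decision line. What is at stake is the study's main statement on precision, which would have no controlled error rate.

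**Working it through.** The plan states no power or precision figure, so there is none to reproduce.

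**Inputs**
- Section 3.0: "We seek to enroll a total of 85 paid volunteers", and the first 5 are left out of the final analysis. 85 − 5 = 80, which matches the group sizes in Section 4.0 (40 + 20 + 20).
- Section 7.0: each volunteer has three rest and two stress values. The first two rest scans use one profile each, and the third repeats one of them. Each volunteer therefore gives one same-profile rest pair. The split is not stated; an even split gives about 40 pairs per profile.
- The two stress scans also use one profile each, so there are no same-profile stress pairs.
- Between-profile pairs for hypothesis 3: about 80.

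**Assumptions.** Pooled within-subject (root-mean-square) COV, roughly normal errors, no missing scans, no systematic shift within pairs, and a decision based on the observed COV alone.

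**Interval.** With n pairs, observed COV² is distributed as (true COV)² × χ²(n)/n. For n = 40 the 2.5% and 97.5% points of χ² are 24.43 and 59.34. An observed 10% then has the 95% interval 10 × √(40/59.34) to 10 × √(40/24.43), that is 8.2% to 12.8%.

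**Chance of passing on the observed value.** P(observed ≤ 10%) = P(χ²(n) ≤ n × (10/true)²).

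| True COV | 40 pairs | 80 pairs, no shift between profiles |
|---|---|---|
| 10% | P(χ² ≤ 40.0) = 53% | P(χ² ≤ 80.0) = 52% |
| 11% | P(χ² ≤ 33.1) = 23% | P(χ² ≤ 66.1) = 13% |
| 12% | P(χ² ≤ 27.8) = 7% | P(χ² ≤ 55.6) = 2% |

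Using n − 1 degrees of freedom changes little (23% and 7.5% for 40 pairs at 11% and 12%).

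**Effect of the definition.** If the COV were instead the average of the two-scan COVs of individual volunteers, that average would understate the true value by about 20%. In a simulation with normal errors, the chance of passing with 40 pairs rises to 86% at a true 11% and 63% at 12%.

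**Rule with an upper bound.** One-sided 95% upper bound = observed × √(n/χ²(0.05, n)).
- 40 pairs: √(40/26.51) = 1.228, so the observed COV must be at most 10/1.228 = 8.1%.
- 80 pairs: √(80/60.39) = 1.151, so at most 10/1.151 = 8.7%, if there is no shift.

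The chance of passing is P(χ²(n) ≤ χ²(0.05, n) × (10/true)²). For 40 pairs it is 93% at a true 7%, 80% at 7.5%, 59% at 8%, 21% at 9%, 5% at 10% and 0.9% at 11%.

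**The case against.** The best defence is that this is a check before clinical go-live, described in Section 2.0 as quality assurance and in Section 13.0 as a quality improvement project, where estimation may be enough. The purpose is relevant, but Section 2.0 says the hypotheses will be tested against a number, and Section 7.0 sets a significance level. If only description is meant, the claim should be worded that way.

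Several other objections limit the point, and they stand:

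- The observed-value rule and the pooled COV are assumptions of this review. The plan gives neither, and a sign such as ± does not fit a COV, which cannot be negative. The size depends heavily on the definition.
- The 40-pair figures apply to rMBF only. A reader might carry them over to stress flow, but the design yields no same-profile stress pair.
- The 80-pair figures need a zero mean difference between profiles, which is part of what hypothesis 3 examines.
- Under the pooled COV, the risk at a true 12% is modest (7% or 2%). The 11% case carries the argument.
- The bound passes a camera equal to the benchmark only 5% of the time. That is demanding, so the weaker conclusion under the fix has to be an acceptable outcome.

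A reader might also infer that a profile would be adopted for clinical use on a false pass. No section ties adoption to a COV below 10%, so the documents do not support that step.

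**Conclusion.** The gap is real: the named analyses cannot answer any of the three hypotheses as worded, and no interval would show how uncertain an observed COV is. For rMBF under hypotheses 1 and 2, a true COV of 11% would be called within 10% about 23% of the time, given the assumptions listed above. For hypothesis 3 the corresponding 13% is only indicative, because a systematic shift between profiles would change it. For sMBF under hypotheses 1 and 2 there is no error rate to quote, because the test-retest COV cannot be estimated from this design. The finding concerns the strength of the precision claim. It does not show that the scanner or either profile is imprecise.

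**What to change.** In Section 7.0:

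1. Define the COV as the pooled within-subject (root-mean-square) COV, and drop the ± sign.
2. For rMBF under hypotheses 1 and 2, report the COV with a confidence interval. Conclude that it falls within 10% only if the one-sided 95% upper bound (chi-square, with a bootstrap check) is below 10%. State the observed value this needs: about 8.1% or less with 40 pairs, updated to the pairs actually obtained.
3. If the bound is not met but the interval includes 10%, conclude only that the result is consistent with the published ±10%.
4. For hypothesis 3, report the mean bolus/low-flow difference with its confidence interval and limits of agreement, alongside the COV bound. Say that the 8.7% threshold for 80 pairs assumes no systematic shift.
5. Restrict hypotheses 1 and 2 in Section 2.0 to rMBF.
6. State how the third rest scan is divided between the profiles.

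This changes text only and needs no extra scans, but it should be fixed before the data are seen. The cost is a stricter claim and the loss of the stress part of hypotheses 1 and 2. With 40 pairs, power is about 80% at a true COV of 7.5% and 21% at 9%, so a camera only slightly better than the benchmark will usually earn the weaker conclusion.
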